6.4.2 Analysis of Immunogenicity Endpoints

The immunogenicity endpoints are defined in Section 2.

- GMT and the geometric mean fold increase (GMFR) in serum antibody titer post-vaccination over Day 1 (baseline) at Days 7, 28, 35, 56, 112, 224 and 336 (Phase 1a, groups G1, G2 and G3); at Days 7, 14, 28, 56, 84, 168 and 336 (Phase 1b groups G4 and G5);
 - Neutralizing activity against multiple variant spike protein-expressing pseudovirus, and/or PRNT₉₀ neutralizing activity against wild-type SARS-CoV-2 virus and the variant Beta (B1.351) in all participants.
 - RBD Antibody titers against wild-type variant spike protein measured by ELISA.

Confidence intervals for the difference of geometric means will be included for the pairwise comparison of treatment groups.

The 95% CI for GMTs will be obtained within each group separately. The 95% CI for the mean of log-transformed titer/concentration will be first obtained assuming that log-transformed concentrations/titers are normally distributed with an unknown variance. The 95% CI for GMTs will be then obtained by exponential-transformation of the 95% CI for the mean of log-transformed titers using analysis of variance (ANOVA) model.

SAS® Code for comparing GMTs:

```
PROC MIXED DATA=<Data>; * specify and sub-select data set as applicable;
```

```
*BY Agegrp; * as applicable;
```

```
CLASS trtpn; * other factors may be added, if applicable;
```

```
MODEL AVAL = trtpn; * AVAL=10**titer
```

```
* add factors and options (e.g. ALPHA=.. Solutions) as applicable;
```

```
LSMEANS trtpn / CL ALPHA=0.05 STDERR; * modify/adapt as applicable
```

```
Ods output LSMEANS =_outmix;
```

```
RUN;
```

```
QUIT;
```

```
Data _outmix;
```

```
Set _outmix;
```

GMT= 10**(Estimate);

GMT_LCL = 10**(Lower);

GMT_UCL = 10**(Upper);

RUN;

The GMFR will be derived by using Analysis of Covariance (ANCOVA) to model the difference in the log of the titer values between post vaccination (Day 56) and baseline (Day 0), with treatment group as main effect and baseline titer as covariate. The GMFR will be compared between the treatment groups. Pair-wise comparisons between the treatments groups will be performed using two-sided, 95% confidence, based on the least-squares mean differences from the ANCOVA model.

SAS® Code for comparing GMFR:

```
PROC MIXED DATA=<Data> (analysis dataset);  
class trtpn;  
model diff= trtpn Base; * diff = log10Day56 – log10Day0. Base=log10Day0  
Lsmeans trtpn/cl alpha=0.05;  

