Ods output LSMEANS =_outmix;  
run;  
Quit;  
Data _outmix;  
Set _outmix;  
GMFR = 10**(Estimate);  
GMFR_LCL = 10**(Lower);  
GMFR_UCL = 10**(Upper);  
Run;
```

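### SAP 6.4.2 is inconsistent on whether each group's GMT 95% interval uses that group's own variance or one pooled over groups, so the reported intervals can be too narrow or too wide

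*SAP*

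**What the plan says.** SAP 6.4.2 describes the GMT interval in three ways.

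- The text states: "The 95% CI for GMTs will be obtained within each group separately". It takes log titers to be "normally distributed with an unknown variance".
- The last sentence of that paragraph obtains the GMT limits by back-transforming the interval "for the mean of log-transformed titers using analysis of variance (ANOVA) model".
- The sample code fits "MODEL AVAL = trtpn; * AVAL=10titer" and takes the limits from "LSMEANS trtpn / CL ALPHA=0.05 STDERR". Treatment is a CLASS factor. There is no REPEATED / GROUP= statement and no BY treatment. Comments in the code allow it to be adapted.

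The section also promises between-group intervals: "Confidence intervals for the difference of geometric means will be included for the pairwise comparison of treatment groups".

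Protocol 4.13 makes point estimates and 95% intervals, tabulated by study group, the form in which immunogenicity is reported. Protocol 10.3 calls the immunogenicity results exploratory. Neither document gives an SD for log titers.

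**The concern.** As written, PROC MIXED estimates one residual variance and uses it, with its pooled degrees of freedom, for every group's limits. That is not an interval obtained separately within each group. Two programmers could follow the section in good faith and produce different tables, and the permission to adapt the code does not say which variance is meant.

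The choice matters most in Phase 1a. There an unvaccinated group given saline (G3) is modelled with two vaccinated groups. If the placebo titers cluster near the assay floor, which is an assumption, they pull the pooled variance down. The pooled limits would then be too tight for a more variable vaccine group and too loose for placebo. What is at stake is whether the tabulated intervals really have 95% coverage.

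**Working it through.** **Inputs from the documents.** Two-sided 95% level (SAP 6.4.2). Phase 1a: 20 per group (SAP 3), or 20 × 0.9 = 18 at about 10% drop-out. Phase 1b: 27 per group (SAP 3), or 48 / 2 = 24 completers (SAP 3.3).

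**Assumptions.** Log10 titers are normal. Phase 1a and Phase 1b are modelled separately. All SDs and SD ratios are assumed.

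**Formulas.** On the log10 scale the limits are mean ± t·s/√n.
- Own variance: s is the group's SD, with n − 1 df.
- Pooled code: s² is the average of the group variances (equal n), with 3n − 3 df in Phase 1a and 2n − 2 in Phase 1b.
- Coverage for group g is the average of 2Φ(t·s/SD_g) − 1 over the sampling distribution of s.

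**The plan's own figure.** Own variance gives 95.0% at n = 20 and at n = 18, whatever the other groups' SDs. The pooled code gives 95.0% when all SDs are equal.

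**When G2 is affected.** The expected pooled variance is (SD_G1² + SD_G2² + SD_G3²)/3. It is below SD_G2² exactly when 2·SD_G2² > SD_G1² + SD_G3². As a boundary for coverage this is approximate: at equality with SD_G1 different from SD_G3, coverage is 94.7 to 95.0%. With unequal n the variances are weighted by n − 1.

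**Phase 1a, SD_G1 = SD_G2, n = 20** (n = 18 agrees to the whole percent):

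| SD_G3/SD_G2 | pooled SD / SD_G2 | G2 coverage | G3 coverage |
|---|---|---|---|
| 0 | √(2/3) = 0.816 | 89.0% | see below |
| 0.5 | √(2.25/3) = 0.866 | 91.1% | 99.9% |
| 0.75 | √(2.5625/3) = 0.924 | 93.0% | 98.3% |
| 1 | 1 | 95.0% | 95.0% |

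The G1-versus-G2 interval scales its standard error by the same pooled SD, so it misses 11, 9, 7 and 5% of the time in these four rows.

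**Width, assuming SD 0.5 in G1 and G2, n = 20.** Own variance: 2.093 × 0.5/√20 = 0.234, so the G2 GMT is given to within a factor of 10^0.234 = 1.71. Pooled, placebo SD 0: 2.002 × 0.408/√20 = 0.183, a factor of 1.52. The other three rows give 1.56, 1.61 and 1.67. With placebo SD 0, the code also prints a factor of 1.52 around a placebo GMT whose values are all identical.

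**Direction depends on G1 as well as placebo** (n = 20):
- G1/G2 SDs 0.3/0.5, placebo 0 to 0.375: G2 coverage 81 to 88%.
- G1/G2 SDs 0.5/0.3, placebo 0 to 0.225: G2 coverage 97 to 98%.

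**Phase 1b, n = 24 to 27.** SD_G5/SD_G4 of 0.5, 0.75, 1 and 1.25 gives G4 coverage of 87.9, 91.8, 95.0 and 97.2%. The G4-versus-G5 GMT contrast keeps an error of 5.0 to 5.2%.

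**Response label.** Read as SAS, the comment sets the response to ten raised to the titer. That overflows double precision from a titer of 309. The output is back-transformed as ten to the power of the estimate, so log10(titer) is required: titers 20, 40 and 80 then return a GMT of 40.

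**The case against.** The strongest reply is that there is no contradiction. The paragraph names ANOVA, a one-way ANOVA with common variance is what the code fits, and the phrase about separate intervals may only mean one interval per group rather than one per contrast. This shows that the text is mixed, and pooling may have been intended. It does not remove the problem. A reader of the separate-intervals sentence would expect own-group variances, the section does not settle the point, and pooling a saline group with vaccinated groups can give the wrong limits for both.

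It is also fair that the code is an adaptable template. The response label and the missing DIFF option are therefore clerical slips and would not survive programming.

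It is fair too that, without SDs, neither the direction nor the size of the error is known. Differences of moderate size have small effects. In Phase 1b, floor clustering in G5 is not expected, because those participants have had two mRNA doses.

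The GMFR analysis might seem to share the fault, since its limits are also back-transformed from one model ("GMFR_LCL = 10(Lower"). It does not. Its text specifies comparisons "based on the least-squares mean differences from the ANCOVA model", and its code does that. Equal-variance ANCOVA is a conventional choice there.

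**Conclusion.** The inconsistency is on the face of SAP 6.4.2 and should be fixed. Its numerical effect is conditional. Under the SD ratios assumed above, G2 coverage in Phase 1a runs from 81% to 98% and G4 coverage in Phase 1b from 88% to 97%. All these figures assume normal log titers, equal group sizes within a phase, and each phase modelled alone.

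Three stronger conclusions are tempting and are not supported:
- That the vaccine groups' intervals will be too narrow. No SD is stated, and a small placebo SD alone is not enough, because a sufficiently large G1 SD makes G2's interval too wide.
- That a go/no-go decision would be wrong. The protocol refers to non-inferiority of GMTs against convalescent sera, but it gives no margin and ties no continuation rule to these limits. The results are descriptive and exploratory.
- That the reported GMTs are wrong. The group means, and so the point GMTs, are the same under either variance.

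The consequence is limited to the accuracy of the reported 95% intervals.

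**What to change.** In SAP 6.4.2:

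1. Compute each group's GMT interval from that group's own log10 variance, either as a one-sample t interval by group or with REPEATED / GROUP=trtpn and Satterthwaite degrees of freedom. Align the ANOVA sentence with this.
2. Allow group-specific variances in the promised pairwise GMT comparisons, and report them as GMT ratios, since a back-transformed log difference is a ratio.
3. Add a fallback for a placebo group whose titers are all at the assay floor: report that value without an interval, and base the ratio to placebo on the vaccine group's variance.
4. Clerical: change the comment to AVAL = log10(titer) and add DIFF to LSMEANS.

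Stating the equal-variance assumption of the GMFR ANCOVA is optional.

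The cost is SAP wording and code only. If the SDs are in fact equal, the vaccine-group intervals become about 4% wider in Phase 1a and 2% wider in Phase 1b on the log scale, because each group uses fewer degrees of freedom.

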4.13 Immunogenicity Assessments

Immunogenicity will be assessed by measuring serum nAb titers against wild-type SARS- CoV-2 virus (PRNT) and/or spike protein-expressing pseudovirus (microneutralization), serum binding antibody titers against spike protein and the spike protein receptor-binding domain (RBD) and peripheral blood mononuclear cell (PBMC) T cell responses against spike protein. Testing will include assessment of responses against spike protein of the original SARS-CoV-2 isolate as well as spike protein of variant Beta (B.1.315) and other variants. In Phase 1a, time points for evaluation will be at Study Days 1, 7, 28,

35, 56, 112, 224 and 336. In Phase 1b, time points for evaluation will be at Study Days 1, 7, 14, 28, 56, 84, 168 and 336. Neutralizing antibody and binding antibody results will be presented as the geometric mean titer (GMT) and the geometric mean fold increase in titer post-vaccination over baseline. T cell responses will be presented as the geometric mean number of IFN- γ ELISPOT-positive cells per 10^6 PBMCs.

A non-inferior GMT nAb titer against the GMT of the panel of COVID-19 convalescent sera (tested against the original Wuhan strain PNA for Phase 1a participants and against the B.1.351 beta variant PNA in Phase 1b) in subjects receiving 2 doses of VBI-2902a will justify proceeding with further clinical development; comparison of the nAb GMT against the WHO reference standard will be used to aid benchmarking against other COVID-19 vaccine candidates.

Similarly, the immunogenicity of VBI-2905a booster in previously vaccinated will be assessed in G4 participants by comparing it to G5 participants. A four-fold increase in the post-boost neutralizing antibody titer in the beta variant PNA will be considered as a confirmatory benchmark to advance clinical development of the 2905a vaccine candidate. If the results are not confirmatory, then the analysis of the RBD ELISA and IgG and T cell data will be undertaken by the SSC to make a decision to further the development of 2905a.

Immunogenicity results will be presented descriptively as point estimates and 95% confidence intervals (CIs), which will be tabulated by study group. Exploratory immunogenicity endpoints may include GMTs against variants of concern, as well as additional markers for T cell responses by ELISPOT and serum binding IgG subclasses as a marker of Th1 (IgG1 and IgG3) and Th2 (IgG4) dominated responses.

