The SSC will review unblinded immunogenicity data 7 days and 28 days after the first vaccinations (Groups G4 and G5).

A total of 54 healthy adults, age 18-54 years, with no history of clinical or laboratory diagnosis of SARS-CoV-2 infection or COVID-19 illness, will be enrolled in the Phase 1b part of the study. All participants in Phase 1b will have been previously vaccinated with an authorized mRNA COVID-19 vaccine, including the second dose administered at least 4 months prior to enrollment. Participants will be randomized at a 1:1 ratio to receive, in a blinded fashion, one dose of VBI-2905a or placebo:

- **Group G4** – 27 participants who had previously received a full course (2 doses) of an authorized S protein mRNA COVID-19 vaccines, with the second dose administered at least 4 months prior to the enrollment into the study, will receive VBI-2905a at a dose of 5 µg of S protein at Day 1.
- **Group G5** – 27 participants who had previously received a full course of an authorized S protein mRNA COVID-19 vaccines at least 4 months prior to the enrollment into the study, will receive placebo at Day 1.

[figure not shown]

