3.3 Sample Size and Power

A total of approximately 60 participants will be enrolled in Phase 1a and approximately 54 participants in Phase 1b. Participants in Phase 1a will be randomized at 2:1 to VBI-2902a or placebo. Participants in Phase 1b who have been previously vaccinated with COVID-19 mRNA vaccine will be randomized at 1:1 to receive one dose of VBI-2905a (group G4) or placebo (group G5) at Day 1

The Phase 1a and phase 1b parts of the study are being conducted at clinical sites in Canada. For the Phase 1b part of the study, the sites will only enroll participants who have previously received mRNA COVID-19 vaccines.

With ~10% drop-out rate it is estimated that at least 56 participants will complete Phase 1a and 48 participants will complete Phase 1b. The sample size per active group will allow for the detection of at least a two-fold difference in neutralizing antibody (nAb) titers with 80% power and an alpha error of 0.05.

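### SAP 6.4.2 states a baseline-adjusted titer model for Day 56 only, leaving the G4 v G5 contrast at the other six Phase 1b visits without one

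*SAP*

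**What the plan says.** SAP 6.4.2 lists GMT and GMFR as Phase 1b endpoints at Days 7, 14, 28, 56, 84, 168 and 336 and gives two models.

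- **GMT.** The code line is "MODEL AVAL = trtpn". Treatment is the only term. Comments beside it allow further factors if applicable, but none is named.
- **GMFR.** An ANCOVA is used to "model the difference in the log of the titer values between post vaccination (Day 56) and baseline (Day 0"), with treatment as main effect and baseline titer as covariate. The code forms the difference from Day 56 and baseline. Pairwise contrasts are made "using two-sided, 95% confidence, based on the least-squares mean differences from the ANCOVA model".

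Protocol 4.13 says that the immunogenicity of the booster "will be assessed in G4 participants by comparing it to G5 participants". SAP section 3 has the SSC review unblinded G4 and G5 immunogenicity at 7 and 28 days after vaccination. SAP 3.3 claims "detection of at least a two-fold difference in neutralizing antibody (nAb) titers with 80% power and an alpha error of 0.05". It gives no SD, and Protocol 10.3 says that no formal power calculation is reported.

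**The concern.** Every Phase 1b participant has had two mRNA doses, the second at least 4 months before enrollment, with no upper limit on the interval. Day 1 titers can therefore carry real information about later titers, above all in G5, which receives only saline. The SAP accepts the principle by adjusting for baseline at Day 56.

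At the other six visits, a programmer following the code as written would compare G4 with G5 without the Day 1 titer. Whatever part of the between-person spread Day 1 could explain stays in the error term, and a chance difference between the arms at Day 1 passes into the ratio. Two of those six visits are the ones that the SSC sees.

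**Working it through.** **Inputs from the documents**
- Phase 1b size: "A total of 54 healthy adults, age 18-54 years", "randomized at 1:1 to receive one dose of VBI-2905a (group G4) or placebo (group G5) at Day 1", so 27 per arm.
- Completers: "With ~10% drop-out rate it is estimated that at least 56 participants will complete Phase 1a and 48 participants will complete Phase 1b". For Phase 1b, 54 × 0.9 = 48.6, in line with 48, or about 24 per arm.
- Effect: two-fold, log10(2) = 0.301. Alpha is 0.05, taken as two-sided to match the contrasts in SAP 6.4.2.

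**Assumed, because the documents give no value**
- SD of log10 titer, equal at Day 1 and post-dose.
- Correlation r between Day 1 and post-dose log10 titer.

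**1. The plan's own figure.** Without an SD, the 80% power can be neither reproduced nor refuted. It can be inverted: SD = 0.301 / [(1.960 + 0.842) × √(2/n)].
- n = 27: 0.301 / (2.802 × 0.2722) = 0.395
- n = 24: 0.301 / (2.802 × 0.2887) = 0.372

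I use 0.372, the value consistent with the claim at 24 per arm, and 0.5 as a less favourable assumption.

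**2. Effect of adjustment on the SE.** Unadjusted SE = SD × √(2/n). The adjusted SE is that value times √(1 - r²) × √(1 + 1/(2n - 4)). The last factor is the average cost of estimating the slope; at n = 24 it is √(1 + 1/44) = 1.011. Break-even is at r² = 1/45, so r is about 0.15.

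**3. Results at 24 per arm.** Power is for a two-fold ratio from the noncentral t, with 46 df unadjusted and 45 df adjusted. The CI factor is the multiply/divide half-width of the 95% interval for the ratio.

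| Model | SE change | Power, SD 0.5 | CI factor, SD 0.5 | Power, SD 0.372 | CI factor, SD 0.372 |
|---|---|---|---|---|---|
| Treatment only | reference | 53% | 1.95 | 78% | 1.65 |
| Adjusted, r = 0 | +1.1% | 52% | 1.97 | 77% | 1.66 |
| Adjusted, r = 0.3 | -3.5% | 56% | 1.91 | 81% | 1.62 |
| Adjusted, r = 0.5 | -12.4% | 64% | 1.80 | 88% | 1.55 |
| Adjusted, r = 0.7 | -27.8% | 81% | 1.62 | 97% | 1.43 |

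Without the slope penalty the last two SE changes are -13.4% and -28.6%. The 78% at SD 0.372 is the t-based counterpart of the normal-approximation 80%.

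**4. Unequal correlations.** A vaccine response may weaken the link with Day 1 in G4 but not in G5. In 20,000 simulated trials at SD 0.372, r = 0.3 in G4 and 0.8 in G5 gave 90.1% power adjusted against 78.3% unadjusted. With r = 0 in G4 and 0.8 in G5 it was 84.8% against 78.9%.

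**5. Chance imbalance.** At SD 0.5, one SE of the Day 1 difference between arms is 0.5 × 0.2887 = 0.144 log10, a 1.39-fold ratio. At r = 0.7 this moves the unadjusted post-dose ratio by 10^(0.7 × 0.144), about 1.26-fold.

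**6. Day 56.** Regressing the log difference on treatment and baseline gives the same treatment coefficient and SE as regressing the post-dose log titer on them; only the baseline slope changes, by exactly one. The planned Day 56 GMFR ratio therefore is the baseline-adjusted GMT ratio.

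**7. A fold rise without the covariate is no substitute.** The variance of its between-arm contrast is 2(1 - r) times that of the treatment-only model, so it is less precise whenever r is below 0.5.

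The figure of 24 is the planned completer count. Early visits may have up to 27 per arm. Later visits may have fewer than 24, because SAP 4.4 censors titers after a non-study vaccine or infection.

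**The case against.** **Day 56 may be a worked example.** SAP 6.4.2 lists GMFR at every visit, gives ANCOVA as its only GMFR method, and marks the GMT code as adaptable. This stands in part: adjustment at other visits is unspecified rather than ruled out. But nothing says that the model extends beyond Day 56, and an optional, unnamed factor is not prespecification. Both phases are unblinded after Day 56, so a covariate chosen then for Days 84, 168 and 336 would be chosen with the data open.

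**Day 56 is the interim reporting point and is already adjusted.** This stands. A reader might also take the two Day 56 contrasts as an error. They are not one: GMT and GMFR are separately defined endpoints. What is missing is a statement of which gives the between-group result.

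**Immunogenicity is descriptive and exploratory.** Protocol 4.13 promises point estimates with 95% intervals, and its benchmark for advancing VBI-2905a is a four-fold rise in titer. No decision threshold rests on an unadjusted G4/G5 ratio. This stands and limits the stakes, although interval width is just what a descriptive analysis delivers.

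**The correlation is unknown.** This also stands. A reader might infer that precision is lost at every other visit, that Day 1 titers vary widely, or that the trial has only 53% power. The documents support none of these: they give no correlation, no titer distribution and no SD, and the 53% comes from an assumed SD of 0.5.

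**Conclusion.** The point holds as a gap in the specification with a conditional cost. Six of the seven Phase 1b post-dose visits, including both SSC review visits, have no stated baseline-adjusted model, and the GMT code as written uses treatment alone. If r is below about 0.15, nothing is lost. The SE could be cut by roughly an eighth at r = 0.5 and by more than a quarter at r = 0.7. Some correlation is plausible in a primed population with a saline arm, but its size at each visit, and any change between Day 7 and Day 336, is assumed here. The balance still favours adjusting, since the worst case is about 1% on the SE and one point of power. The change is worthwhile; the planned analysis is not invalid without it.

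**What to change.** In SAP 6.4.2, prespecify for every post-dose visit: log10 titer = treatment + log10 Day 1 titer. Report the adjusted G4/G5 GMT ratio with its 95% CI as the between-group result, and state that it is identical to the adjusted GMFR ratio. Keep unadjusted GMTs as within-group descriptions. Apply the same model to the Day 7 and Day 28 SSC outputs.

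The cost is a short text and code change and one degree of freedom per model. Day 1 sera are already scheduled. Little gain is expected in Phase 1a, where participants have no prior COVID-19 vaccine or known infection.

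In the same edit, correct the comment that defines AVAL in the GMT code. It sets the response to ten raised to the titer, whereas the text and the back-transformation of the estimates both require log10 of the titer.

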10.1.2 Secondary Endpoints/Outcome Measures

Rate and severity of unsolicited AEs throughout the study

Rate and severity of medically-attended adverse events (MAAEs) throughout the study Rate of serious adverse events (SAEs) throughout the study

Rate and severity of laboratory abnormalities (hematology, biochemistry, urinalysis) throughout the study

- GMT and the geometric mean fold increase in serum antibody titer post-vaccination over Day 1 (baseline) at Days 56 and 224 (Phase 1a) or Days 56 and 168 (Phase 1b):
 - Neutralizing activity against multiple variant spike protein-expressing pseudovirus, and/or PRNT neutralizing activity against wild-type SARS-CoV-2 virus and the variant Beta (B.1.351) in all participants
 - RBD antibody titers against wild-type variant spike protein measured by ELISA
- GMT and the geometric mean fold increase in serum antibody titer post-vaccination over Day 1 (baseline) at Days 7, 28, 35, 56, 112, 224 and 336 (Phase 1a); Days 7, 14, 28, 56, 84, 168 and 336 (Phase 1b)
 - Neutralizing activity against multiple variant spike protein-expressing pseudoviruses, and/or PRNT neutralizing activity against multiple variants of SARS-CoV-2 virus and the variant (B.1.351) in all participants
 - RBD antibody titers against wild-type variant spike protein measured by ELISA

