6.4.1 Immunogenicity Evaluations

Immunogenicity will be assessed by measuring serum nAB titers against wild-type SARS-CoV-2 virus (PRNT) and/or spike protein-expressing pseudovirus (microneutralization), serum binding antibody titers against spike protein and the spike protein receptor-binding domain (RBD), and peripheral blood mononuclear cell (PBMC) T cell responses against spike protein.

Testing will include assessment of responses against spike protein of the original SARS-CoV-2 isolate as well as spike protein of variant Beta (B.1.315) and other variants. In Phase 1a, time points for evaluation will be at Study Days 1, 7, 28, 35, 56, 112, 224 and 336. In Phase 1b, time points for evaluation for groups G4 and G5 will be at Study Days 1, 7, 14, 28, 56, 84, 168 and 336.

Neutralizing antibody and binding antibody results will be presented as the geometric mean titer (GMT) and the geometric mean fold increase in titer post-vaccination over baseline. T cell responses will be presented as the geometric mean number of IFN-ELISPOT-positive cells per 10^6 PBMCs.

Geometric mean nAb titers and antibodies to the receptor binding domain (RBD) for 5 µg and 10 µg dose groups at Day 1, 7, 28, 35 and 56 will be compared to each other and pooled COVID-19 convalescent serum to select the optimal dose of VBI-2902a in the age cohorts.

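### SAP 6.4.2 reports each group's GMFR as an ANCOVA least-squares mean at a shared baseline with a pooled-variance interval, not as the group's own fold increase over Day 1, and does not say that the two phases are modelled separately

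*SAP*

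**What the plan says.** The protocol (10.1.2) lists as a secondary endpoint "GMT and the geometric mean fold increase in serum antibody titer post-vaccination over Day 1 (baseline"), and protocol 4.13 has immunogenicity results tabulated by study group with 95% intervals. SAP 6.4.1 repeats the measure as "the geometric mean fold increase in titer post-vaccination over baseline". Neither passage mentions baseline adjustment. The protocol gives no estimator and leaves methods to the SAP (10.6).

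SAP 6.4.2 then sets the estimator: "The GMFR will be derived by using Analysis of Covariance (ANCOVA) to model the difference in the log of the titer values" between Day 56 and baseline, "with treatment group as main effect and baseline titer as covariate". The model line is "model diff= trtpn Base; * diff = log10Day56 – log10Day0. Base=log10Day0". The least-squares means are requested with no option fixing the covariate value, and the GMFR and its limits are 10 raised to each least-squares mean and its limits.

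Three further features matter:
- The text promises pairwise comparisons from least-squares mean differences, but the code requests no differences and outputs only the per-group means.
- The input data set is a placeholder. The GMT code carries a note about sub-selecting the data; the GMFR code does not.
- SAP section 7 declares no change from the protocol's analyses.

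**The concern.** A fold increase over Day 1, tabulated for a group, would ordinarily be read as that group's own mean log change, back-transformed. A least-squares mean from a model with baseline as covariate answers a different question: what the group's change would be at a baseline common to everyone in the model. Adjustment of this kind suits a comparison between groups. It is not needed for a within-group description, and it breaks the link between the printed GMFR and the printed GMTs.

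Two things are at stake. First, the interval: one residual variance serves all groups, although saline recipients may vary much less in their change than vaccine recipients. Second, the model's scope: Phase 1a enrols people with no COVID-19 vaccination and Phase 1b enrols people who have had two mRNA doses. If both phases entered one model, every group would be evaluated at an intermediate baseline typical of neither phase.

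**Working it through.** The plan gives no figure for this model: no baseline titer, no baseline SD and no slope. The nearby power statement (two-fold, 80%, alpha 0.05) concerns titer differences and gives no SD, so it cannot be used here.

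**Identity.** Let b be the common slope of log10 rise on log10 baseline. With the covariate at its overall mean, the default when none is specified,

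LS mean of group g − raw mean change of group g = b × (overall baseline mean − baseline mean of group g).

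The reported GMFR is the raw GMFR times 10 to that power. The GMT model has no covariate, so on log10 titers with complete data Day 56 GMT / Day 1 GMT equals the raw GMFR exactly. The adjusted figure matches it only if b is zero or the group's baseline mean equals the overall mean.

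**Phase 1b fitted alone (27 per arm).** G4's baseline mean differs from the overall mean by half the arm difference, whose standard error is SD × √(2/27) / 2. With an assumed SD of 0.4 this is 0.0544, and 1.96 × 0.0544 = 0.107. The 95% bound on the factor is 10^(|b| × 0.107):

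| b (assumed) | 95% bound on reported/raw |
|---|---|
| -0.3 | 1.08 |
| -0.5 | 1.13 |
| -0.8 | 1.22 |

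The factor is centred on 1. Simulated Phase 1b fits with raw GMFRs of 4.0 (G4) and 1.0 (G5) returned 4.0 and 1.0 on average.

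**Phase 1a fitted alone (20 per group).** If naive baselines sit at the assay floor (assumption), the shift is close to nil. With the same SD of 0.4, the bound is 10^(|b| × 1.96 × 0.4 × √(1/20 − 1/60)), which is 1.18 at b = -0.5.

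**Interval.** For two equal arms, setting the covariate aside, the pooled SD is √((s_vaccine² + s_placebo²)/2). With assumed SDs of 0.4 and 0.1 it is √((0.16 + 0.01)/2) = 0.292, or 0.73 of the vaccine arm's own SD. Coverage for the vaccine group is then about P(|Z| < 1.96 × 0.73) = 85%. As the placebo SD tends to zero the ratio tends to 0.707 and coverage to 83%. With equal SDs nothing is lost. Simulation under assumed unequal variances agreed: about 84% for G4 from the least-squares mean interval, about 95% from G4's own t interval.

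**All five groups in one model.** The enrolment weights are 60/114 = 0.526 and 54/114 = 0.474. With D the Phase 1b minus Phase 1a gap in mean log10 baseline, Phase 1b values are multiplied by 10^(−b × 0.526 × D) and Phase 1a values by 10^(b × 0.474 × D).

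| D (assumed) | b (assumed) | Phase 1b | Phase 1a |
|---|---|---|---|
| 0.5 | -0.2 | ×1.13 | ×0.90 |
| 1.0 | -0.2 | ×1.27 | ×0.80 |
| 1.0 | -0.5 | ×1.83 | ×0.58 |
| 1.0 | -0.8 | ×2.64 | ×0.42 |
| 1.5 | -0.5 | ×2.48 | ×0.44 |
| 1.5 | -0.8 | ×4.28 | ×0.27 |

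At D = 1.0 and b about -0.5, simulated pooled fits reported a true G4 value of 4.0 as 7.1, an unchanged G5 as 1.8 and an unchanged G3 as 0.6. The G4-versus-G5 contrast was the same in the pooled and Phase 1b-only fits.

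**The case against.** The strongest reply is that nothing in the SAP says the phases share a model. SAP section 2 and 6.4.2 list the endpoint by phase with different visit days, the phases test different products in different populations, each phase is unblinded after its own Day 56 review, and the code's data set is a placeholder. Separate models are at least as natural a reading. This stands, so the large multipliers are conditional. What remains is that the SAP does not say so, and since Day 56 is common to both phases a pooled run would execute without error.

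A second reply is that the protocol sets no estimator, so an adjusted mean is a permissible choice and, within a randomized phase, agrees with the raw value in expectation. That stands for the point estimate. It does not cover the pooled-variance interval or the mismatch with the tabulated GMTs.

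A reader might also infer that a G4 rise of two-fold could be declared four-fold and so meet the benchmark for VBI-2905a in protocol 4.13. The documents do not support that. The benchmark is not tied to this model's output and follows directly on the G4-versus-G5 comparison, which is unaffected. Protocol 4.4 also expresses the four-fold measure as a percentage of subjects, which does not use the ANCOVA. The steering committee's Phase 1b reviews are at 7 and 28 days, whereas the written model is for Day 56. A pooled fit would also show itself through apparent change in the placebo groups.

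**Conclusion.** The point holds as a mismatch between estimator and endpoint, plus an omission about model scope. As coded, the per-group GMFR is a baseline-adjusted value at a shared baseline with a pooled-variance interval, and the between-group ratio that the text promises is not output.

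Fitted by phase, the effect on the estimate is modest and without systematic direction: about 10% to 20% at the 95% bound in Phase 1b, given an assumed baseline SD of 0.4 log10 and the slopes shown. The interval for a vaccine group can be too narrow if placebo changes vary much less.

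Fitted across phases, every group's GMFR would be misstated, by a factor anywhere from slight to more than four depending on a gap and slope that the documents do not give. It would be tempting to say that the values are off by about two-fold. That needs the pooled model together with, for example, a gap of 1.14 log10 at slope -0.5, and it is not a figure the plan supports. The edit is worth making before analysis because it is cheap and removes both issues.

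**What to change.** In SAP 6.4.2:
1. Derive each group's GMFR at each visit as 10 to the power of the mean of (log10 post-vaccination titer − log10 Day 1 titer), among participants with both values. Take the 95% CI from that group's own t interval on the log scale.
2. Keep the baseline-adjusted ANCOVA only for the between-group GMFR ratio, and add the request for least-squares mean differences and their limits to the code, so that the promised comparison is produced.
3. State that models are fitted separately for Phase 1a (G1 to G3) and Phase 1b (G4 and G5).

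The cost is a few lines of SAP text and code. No new data are needed and the ANCOVA is retained for the purpose it suits. The raw GMFR then agrees with the ratio of GMTs when data are complete, and a placebo group with no observed mean change is reported as unchanged.
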